6.4.2 Secondary Efficacy Endpoints

The secondary efficacy endpoints are as follows:

- Time to improvement of at least 2 categories relative to baseline on a 7-category ordinal scale of clinical status
- Time to hospital discharge or “ready for discharge” (as evidenced by normal body temperature and respiratory rate, and stable oxygen saturation on ambient air or ≤ 2 L supplemental oxygen)
- Duration of supplemental oxygen
- Proportion of patients alive and free of respiratory failure (requiring non-invasive ventilation, high-flow oxygen, invasive mechanical ventilation, or ECMO) at Day 28
- *Clinical status assessed using a 7-category ordinal scale at Days 14 and 28*
- Incidence of invasive mechanical ventilation *or* ECMO
- Ventilator-free days to Day 28
- Incidence of ICU stay
- Duration of ICU stay
- Time to clinical failure, defined as the time to death, invasive mechanical ventilation, ICU admission, or withdrawal of care (whichever occurs first). For patients entering the study already in ICU or on invasive mechanical ventilation, clinical failure is defined as a one category worsening on the ordinal scale, withdrawal, or death.
- Mortality rate at Days 14 and 28
- *Time to clinical improvement, defined as a NEWS2 of ≤ 2 maintained for 24 hours*

The secondary endpoints will be analyzed in the mITT population. Statistical models will be adjusted for the covariates as described in Section [6.4](#).

Full details of hypothesis testing, analysis methods, type I error control, and missing data handling will be documented in the DAP.

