3.3.3 Rationale for Patient Population

Approximately 15%–20% of patients with COVID-19 pneumonia have severe disease requiring hospitalization and supplemental oxygen and 5% of patients with COVID-19 pneumonia will be admitted to the ICU (WHO 2020b). Risk factors for progression to severe COVID-19 pneumonia are common and include advanced age, cardiovascular disease, diabetes mellitus, chronic lung disease, and chronic kidney disease (Liang et al. 2020; Wu et al. 2020; Zhou et al. 2020). In a study of 138 hospitalized patients with COVID-19 pneumonia in China, 26% of patients required transfer to the ICU and 4.3% of patients died (Wang et al. 2020). In a second study of 1099 Chinese patients with

MSTT1041A/UTTR1147A—Genentech, Inc.
41/Protocol GA42469, Version 4

COVID-19 pneumonia, 5% of patients were admitted to the ICU, 2.3% of patients underwent invasive mechanical ventilation, and 1.4% of patients died (Guan et al. 2020). Patients with severe COVID-19 pneumonia requiring hospitalization and supplemental oxygen have significant morbidity and mortality and despite multiple experimental therapies in wide use, there are no treatments with proven efficacy to date. This study will enroll patients hospitalized with severe COVID-19 pneumonia requiring supplemental oxygen at high risk of developing ARDS, hypoxic respiratory failure and death.

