4.1.1 Inclusion Criteria

Patients must meet the following criteria for study entry:

- Documented informed consent as described in Section [4.5.1](#)
- Age ≥ 18 years at time of signing Informed Consent Form

MSTT1041A/UTTR1147A—Genentech, Inc.
42/Protocol GA42469, Version 4

- Ability to comply with the study protocol
- Hospitalized with COVID-19 pneumonia confirmed per WHO criteria (including a positive PCR of any specimen; e.g., respiratory, blood, urine, stool, other bodily fluid) and evidenced by chest X-ray or CT scan
- For sites at an altitude \leq 5000 feet: peripheral capillary oxygen saturation (SpO_2) \leq 93% or partial pressure of oxygen (PaO_2)/fraction of inspired oxygen (FiO_2) \leq 300 mmHg or requirement for supplemental oxygen to maintain $\text{SpO}_2 > 93\%$
- For sites at an altitude $>$ 5000 feet: requirement for supplemental oxygen to maintain SpO_2 at an acceptable level per local standard of care
- For women of childbearing potential: agreement to remain abstinent (refrain from heterosexual intercourse) or use contraception, as defined below:

Women must remain abstinent or use contraceptive methods with a failure rate of $< 1\%$ per year during the treatment period and for 95 days after the final dose of study drug.

A woman is considered to be of childbearing potential if she is postmenarchal, has not reached a postmenopausal state (≥ 12 continuous months of amenorrhea with no identified cause other than menopause), and is not permanently infertile due to surgery (i.e., removal of ovaries, fallopian tubes, and/or uterus) or another cause as determined by the investigator (e.g., Müllerian agenesis). The definition of childbearing potential may be adapted for alignment with local guidelines or regulations.

Examples of contraceptive methods with a failure rate of $< 1\%$ per year include bilateral tubal ligation, male sterilization, hormonal contraceptives that inhibit ovulation, hormone-releasing intrauterine devices, and copper intrauterine devices.

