4.5.9 Ordinal Scale Determination

Assessment of clinical status using a 7-category ordinal scale will be recorded *prior to dosing* at baseline on Day 1 and then again once daily every morning (ideally, between 8 a.m. and 12 p.m.) *at subsequent visits* during patient hospitalization. When possible, the patient should be assessed at approximately the same time each day. The ordinal scale categories are as follows:

1. Discharged (or “ready for discharge” as evidenced by normal body temperature and respiratory rate, and stable oxygen saturation on ambient air or ≤ 2 L supplemental oxygen)
2. Non-ICU hospital ward (or “ready for hospital ward”) not requiring supplemental oxygen
3. Non-ICU hospital ward (or “ready for hospital ward”) requiring supplemental oxygen
4. ICU or non-ICU hospital ward, requiring non-invasive ventilation or high-flow oxygen
5. ICU, requiring intubation and mechanical ventilation
6. ICU, requiring ECMO or mechanical ventilation and additional organ support (e.g., vasopressors, renal replacement therapy)
7. Death

In general, patients with oxygen saturation consistently $\leq 90\%$ should be considered for escalation to a higher clinical status category, while patients with oxygen saturation consistently $\geq 96\%$ should be considered for de-escalation to a lower category.

However, actual clinical status category should be recorded on the eCRF. Please refer to the additional guidance for investigators regarding assessment of clinical status using the 7-category ordinal scale.

Patients on supplemental oxygen should be evaluated at least daily and considered for reduction or discontinuation of oxygen support. Actual changes in level of support will be at the discretion of the clinician(s) treating the patient based on the patient's overall condition and may be dictated by other clinical and non-clinical considerations.

Normal body temperature is defined as oral, rectal, axillary, temporal, or tympanic temperature 36.1°C – 38.0°C . Normal respiratory rate is defined as 12–20 breaths per minute.

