6.4.1 Primary Efficacy Endpoint

The primary efficacy objective for this study is to evaluate the efficacy of MSTT1041A compared with placebo and of UTTR1147A compared with placebo, in combination with SOC, on the basis of the following endpoint:

- *Time to recovery, defined as time to score of 1 or 2 on the 7-category ordinal scale (whichever occurs first)*

The ordinal scale categories are as follows:

1. Discharged (or “ready for discharge” as evidenced by normal body temperature and respiratory rate, and stable oxygen saturation on ambient air or ≤ 2 L supplemental oxygen)
2. Non-ICU hospital ward (or “ready for hospital ward”) not requiring supplemental oxygen
3. Non-ICU hospital ward (or “ready for hospital ward”) requiring supplemental oxygen
4. ICU or non-ICU hospital ward, requiring non-invasive ventilation or high-flow oxygen
5. ICU, requiring intubation and mechanical ventilation
6. ICU, requiring ECMO or mechanical ventilation and additional organ support (e.g., vasopressors, renal replacement therapy)
7. Death

Time to recovery will be analyzed using the stratified log-rank test, adjusting for stratification factors. The Kaplan-Meier plot, median time to event, and their 95% CI and p-value from the stratified log-rank test will be presented. A Cox proportional hazards regression model will be used to estimate the hazard ratio comparing MSTT1041A or UTTR1147A with placebo, respectively, adjusting for stratification

MSTT1041A/UTTR1147A—Genentech, Inc.
82/Protocol GA42469, Version 4

factors. Hazard ratios and 95% CIs will be presented. In addition, the *p*-value from unstratified log-rank test, unadjusted hazard ratio, and 95% CI will also be presented. Further details on the primary endpoint analysis will be included in the DAP.

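### A patient who enters in category 2 can never reach the secondary endpoint of a two-category improvement, even if discharged well

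*Protocol*

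**What the plan says.** Protocol Section 6.4.2 lists among its secondary endpoints "Time to improvement of at least 2 categories relative to baseline on a 7-category ordinal scale of clinical status". The synopsis and Section 2.1.2 define it the same way. None of the three adds an alternative for patients who start near the top of the scale.

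On the scale in Sections 4.5.9 and 6.4.1, category 1 is discharged or ready for discharge, and category 2 is "Non-ICU hospital ward (or “ready for hospital ward”) not requiring supplemental oxygen".

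For sites at or below 5000 feet, Section 4.1.1 accepts any one of three findings: SpO2 of 93% or less, PaO2/FiO2 of at most "300 mmHg or requirement for supplemental oxygen to maintain" SpO2 above 93%. For sites above 5000 feet the only route is "5000 feet: requirement for supplemental oxygen to maintain" an acceptable saturation. Section 3.3.3 describes the intended population more narrowly, saying the study will "enroll patients hospitalized with severe COVID-19 pneumonia requiring supplemental oxygen at high risk of developing ARDS".

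Section 4.5.9 asks sites to consider a higher category when saturation stays at or below 90%, but tells them to record the actual category. Section 6.4.2 analyses the secondary endpoints in the mITT population, with no restriction on baseline category.

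**The concern.** The endpoint needs a gain of two categories, but from category 2 only one category is left to gain. If the entry criteria let category 2 patients in, part of the analysis set has no possible event, and the mildest patients are never counted as improved whatever happens to them.

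The consequences would be a cumulative incidence that cannot reach 100%, longer medians in every arm, and a treatment contrast diluted toward no effect. The same list shows that the authors had met this kind of problem: time to clinical failure has a separate definition for patients already in ICU or on invasive ventilation at entry. The two-category endpoint has no such rule.

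**Working it through.** **Step 1. Which patients can have the event.** The largest possible improvement is the baseline category minus 1, and the event needs at least 2.

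| Baseline category | Largest improvement | Event possible |
|---|---|---|
| 2 | 1 | no |
| 3 | 2 | yes |
| 4 | 3 | yes |
| 5 | 4 | yes |
| 6 | 5 | yes |

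A move from 2 to 1 scores 1, which is less than 2.

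**Step 2. Whether category 2 patients can enter.** At sites at or below 5000 feet the three findings in Section 4.1.1 are alternatives, so SpO2 of 93% or less is enough without oxygen use. A ward patient on room air at 91% to 93% is eligible and lies above the 90% level at which Section 4.5.9 suggests considering a higher category. If judged "not requiring supplemental oxygen", this patient is recorded as category 2. Above 5000 feet, where an oxygen requirement is mandatory, category 2 at entry is not expected.

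**Step 3. Illustrated size.** The plan gives no power or event figure for this endpoint, so there is none to reproduce. Inputs borrowed from Section 6.1 (the primary endpoint): 390 patients at 2:2:1:1, hence 130 per active arm and 65 + 65 = 130 on pooled placebo; placebo median 21 days; a 7-day difference, hence 14 days on active; 28 days of follow-up; one-sided 5%. Exponential times are assumed. The share p in category 2 is not given; 1% to 15% is an assumption.

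With p = 0, expected events are 130 × (1 − 0.5^(28/21)) + 130 × (1 − 0.5^(28/14)) = 78.4 + 97.5 = 175.9. Power is Φ(ln 1.5 × √(175.9/4) − 1.645) = Φ(1.04), about 85%.

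With a share p that cannot have the event:

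- patients affected = 390p
- Day 28 incidence = (1 − p) × (1 − 0.5^(28/median))
- displaced median = median × ln[(0.5 − p)/(1 − p)] / ln 0.5
- power from a simulated log-rank test (20,000 replicates, unstratified), with the affected patients kept at risk and event-free to Day 28

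| p | Patients of 390 | Day 28 incidence, placebo / active | Median days, placebo / active | Power |
|---|---|---|---|---|
| 0 | 0 | 60.3% / 75.0% | 21.0 / 14.0 | 85% |
| 1% | 4 | 59.7% / 74.3% | 21.3 / 14.2 | 84% |
| 5% | 20 | 57.3% / 71.2% | 22.6 / 15.1 | 81% |
| 10% | 39 | 54.3% / 67.5% | 24.6 / 16.4 | 75% |
| 15% | 59 | 51.3% / 63.7% | 26.9 / 17.9 | 70% to 71% |

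**Step 4. Sensitivity to handling, at p = 10%.** Restricting the analysis to baseline category 3 or worse gives about 82% instead of 75%. If category 2 patients can have the event but recover quickly with no drug effect (median of 5 days assumed in both arms), power is about 79%. The 85% figure needs them to share the full 14 versus 21 day effect.

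**The case against.** **Few patients may be affected.** Section 3.3.3 describes patients who need oxygen. The PaO2/FiO2 route adds little: a note to Appendix 1 limits protocol arterial gases at screening and Day 1 to ventilated patients with an arterial line. A patient at 93% or below may be judged to need oxygen, or be started on it before the Day 1 score, and is then category 3. Section 4.5.9 also points to additional investigator guidance that is not at hand. This stands, and the true share could be 1% or 2%.

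**The Data Analysis Plan may deal with it.** Section 6.4.2 leaves analysis methods and missing data to that plan. This stands in part: whether these patients are censored, kept at risk or left out is not fixed in the protocol, and Step 4 shows that it matters. But the event itself is defined in the protocol, in three places, and under that definition these patients have no event however they are handled.

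**The harm is limited.** The endpoint is one of twelve secondary endpoints without a stated hierarchy, and the dilution falls on all arms. A move from 2 to 1 is still captured by time to discharge or ready for discharge, and by clinical status at Days 14 and 28. All of this stands.

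A reader might infer more: that first place in the list makes this the leading secondary endpoint, that up to 15 points of power are lost, that the comparison is biased, or that a repair restores 85%. The documents support none of these. No ranking is given. The large losses need a 10% to 15% share, which nothing documents. Chance imbalance in the category 2 share between two arms has an SD of √(2p(1 − p)/130), which is 2.1 points at 3% and 4.4 points at 15%; that is ordinary randomisation noise. The drug effect in these patients is unknown.

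**Conclusion.** The defect holds on the text. As defined, the endpoint is unattainable for any patient entering in category 2. Section 4.1.1 admits such patients at sites at or below 5000 feet, and no other section of the protocol excludes them or gives them an attainable event. The result is dilution of one unranked secondary endpoint, with no inflation of type I error.

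The scale arithmetic is certain; the size is not. The illustrated loss is about 1 point of power at a 1% share, 4 points at 5% and 10 points at 10%. It rests on an assumed share, on medians borrowed from another endpoint, on exponential times and on these patients staying at risk to Day 28. The case for correcting the definition is that it gives a wrong answer for patients who recover, whatever their number.

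**What to change.** In the synopsis and Sections 2.1.2 and 6.4.2, define the event as a gain of two or more categories over baseline or, for patients whose baseline category is 2, reaching category 1. Carry the same rule into the Data Analysis Plan.

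The cost is one sentence in each place. Ordinal scores are already collected at baseline, daily in hospital and at the visits after discharge, so no new data are needed. The downside is small: for these patients the event is a one-step change, so the endpoint mixes one-step and two-step improvements. Restricting the endpoint to baseline category 3 or worse would avoid the mixture, but would drop randomised and treated patients from the comparison.

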2.1.2 Secondary Efficacy Objective

The secondary efficacy objective for this study is to evaluate the efficacy of MSTT1041A compared with placebo and of UTTR1147A compared with placebo, in combination with SOC, on the basis of the following endpoints:

- Time to improvement of at least 2 categories relative to baseline on a 7-category ordinal scale of clinical status
- Time to hospital discharge or “ready for discharge” (as evidenced by normal body temperature and respiratory rate, and stable oxygen saturation on ambient air or ≤ 2 L supplemental oxygen)
- Duration of supplemental oxygen
- Proportion of patients alive and free of respiratory failure (requiring non-invasive ventilation, high-flow oxygen, mechanical ventilation, or ECMO) at Day 28
- *Clinical status assessed using a 7-category ordinal scale at Days 14 and 28*
- Incidence of *invasive* mechanical ventilation or ECMO
- Ventilator-free days to Day 28
- Incidence of ICU stay
- Duration of ICU stay
- Time to clinical failure, defined as the time to death, mechanical ventilation, ICU admission, or withdrawal of care (whichever occurs first). For patients entering the study already in ICU or on mechanical ventilation, clinical failure is defined as a one category worsening on the ordinal scale, withdrawal, or death.
- Mortality rate at Days 14 and 28
- Time to clinical improvement, defined as a National Early Warning Score 2 (NEWS2) of ≤ 2 maintained for 24 hours

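### A low-flow entrant with normal temperature and respiratory rate and stable saturation can meet the ready-for-discharge event unchanged, in the primary endpoint as well as the discharge endpoint

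*Protocol*

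**What the plan says.** Section 4.1.1 gives three alternative oxygenation routes at sites up to 5000 feet: SpO2 at or below 93%, PaO2/FiO2 at or below 300 mmHg, or a "requirement for supplemental oxygen to maintain" SpO2 above 93%. Higher sites need supplemental oxygen to hold saturation "at an acceptable level per local standard of care". No route names a minimum flow. Nothing in Sections 4.1.1 or 4.1.2 requires fever, a raised respiratory rate or a minimum ordinal category.

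Section 6.4.2 lists time to hospital discharge or readiness for discharge, the latter "as evidenced by normal body temperature and respiratory rate, and stable oxygen saturation on ambient air or ≤ 2 L supplemental oxygen". Section 4.5.9 sets normal temperature at 36.1–38.0 °C and adds: "Normal respiratory rate is defined as 12–20 breaths per minute".

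The primary endpoint in Section 6.4.1 is time to a score of 1 or 2. Category 1 contains the same readiness clause. Category 3 is a ward patient "requiring supplemental oxygen", with no flow limit.

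**The concern.** A time-to-event endpoint should start with patients who do not yet have the event. Here some may have it on Day 1. Such patients cannot show a treatment effect through the readiness route. They enter both arms as near-immediate events, shorten the medians and add noise to the log-rank comparison. Randomization is stratified only by invasive ventilation and region, so the stratified test does not separate them out.

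The overlap between categories 1 and 3 adds a scoring problem. The same unchanged patient may be scored 3 on Day 1, as an inpatient on oxygen, and 1 the next morning, as ready for discharge. Time to a 2-category improvement and clinical status at Days 14 and 28 use the same scale and inherit the ambiguity.

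**Working it through.** **Can one patient meet both definitions?** Take a ward patient at a low-altitude site on 2 L, temperature 37.3 °C, rate 18, saturation stable above 93% only with oxygen.

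- Entry: met by the oxygen route.
- Readiness: 37.3 lies in 36.1–38.0; 18 lies in 12–20; saturation is stable on no more than 2 L. Met.
- Ordinal scale: fits category 1 by readiness and category 3 by location and oxygen. Section 4.5.9 has the actual category recorded but does not say which of the two prevails.

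**Does anything in the definition stop this?** Other endpoints in Section 6.4.2 carry a safeguard: the 2-category improvement is relative to baseline, clinical failure has a separate rule for patients already in ICU or ventilated, and the NEWS2 endpoint must hold for 24 hours. The discharge endpoint and time to recovery have no baseline condition, required change or persistence.

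**The plan's own power figure.** Section 6.1 gives medians of 21 and 14 days, 28 days of follow-up, 390 patients at 2:2:1:1 and one-sided 5% alpha. Section 6.4 pools the placebos, so each comparison is 130 v 130. Assuming exponential times:

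- Hazard ratio = 21/14 = 1.5
- Event probability by Day 28: placebo 1 − 2^(−28/21) = 0.603; active 1 − 2^(−28/14) = 0.750
- Events = 130 × (0.603 + 0.750) = 175.9
- Schoenfeld power = Φ(√175.9 / 2 × ln 1.5 − 1.645) = Φ(2.689 − 1.645) = 85.2%

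The stated figure of approximately 80% is not reproduced from the stated inputs alone. An unstated 10–15% loss gives 81.8–79.8%. That is a separate matter; only the change from 85% is used below.

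**Illustration of dilution.** Let a share f of each arm be an event at the first post-baseline assessment, and let the rest follow the 21 v 14 day assumption.

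- Diluted median = m × log2(2(1 − f)). For f = 10%: 21 × 0.848 = 17.8 and 14 × 0.848 = 11.9, a difference of 5.9 days.
- Approximate log-rank mean: U = (1 − f) × 175.9/4 × ln 1.5
- Approximate variance: V = ¼ × [260 f(1 − f) + 175.9(1 − f)]
- For f = 10%: U = 16.05, V = ¼ × (23.4 + 158.3) = 45.4, so z = 16.05/6.74 = 2.381 and power = Φ(2.381 − 1.645) = 76.9%.

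The simulated column is a log-rank test on daily times, 4000 runs per row (Monte Carlo standard error about 0.6–0.7 points).

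| f | Immediate events among 260 | Difference in medians (days) | Power, simulated | Power, approximation |
|---|---|---|---|---|
| 0 | 0 | 7.0 | 85% | 85% |
| 5% | 13 | 6.5 | 82% | 81% |
| 10% | 26 | 5.9 | 76% | 77% |
| 20% | 52 | 4.7 | 69% | 68% |

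**The case against.** **The endpoint is scored by the investigator.** The protocol nowhere says readiness is computed from vital signs. Section 4.5.4 collects one representative set from a single timepoint, which cannot show stability, and no numerical rule for stability is given. The natural reading is first discharge or first score of 1, and Section 4.5.9 refers to additional scoring guidance that is not at hand. This stands in part: a rule separating categories 1 and 3 would help, and the guidance may contain one. It does not settle the matter, because category 1 is defined by the same words and the protocol's own text has no such rule.

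**It belongs in the Data Analysis Plan.** Section 6.4.2 defers hypothesis testing, analysis methods, type I error control and missing data, and Section 6.4.1 defers further analysis detail. Handling of baseline events could be placed there. But the event definition is fixed in the protocol, and as worded it admits unchanged patients.

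**Most low-flow entrants may not qualify.** This stands. A reader might infer that every unchanged patient on 2 L or less is an event. All three criteria must hold, and a febrile or tachypnoeic patient is not one.

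**The size is unknown.** This also stands. A reader might try to derive it by modelling morning temperature and respiratory rate. The documents give no distributions for either, no share of entrants on up to 2 L and no rule for stability, so such a figure would reflect only its assumptions.

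**Conclusion.** The point holds. As written, some patients can satisfy the event definition at entry, in both the discharge endpoint and the primary endpoint. It should be corrected, but it does not invalidate the trial.

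A reader might infer a bias in favour of active treatment. The documents do not support that: assignment is randomized and blinded, so such patients are expected in proportion in every arm. The consequence is a diluted contrast and medians that partly reflect severity at entry.

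The power figures are illustrative. They assume exponential times, equal shares in both arms, and that the 21 and 14 day medians describe the patients who are not immediate events. If the 21-day placebo median already includes such patients, the loss is overstated. They apply to the primary endpoint; the protocol states no power for the discharge endpoint.

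**What to change.** In the synopsis and Sections 2.1.1, 2.1.2, 4.5.9, 6.4.1 and 6.4.2:

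1. Reconcile categories 1 and 3 for ward patients on up to 2 L by stating which takes precedence.
2. Add that a patient who already meets the ready-for-discharge criteria at the pre-dose Day 1 assessment does not have the event through readiness alone without a change from baseline. For example, the event is then actual discharge or, for time to recovery, also coming off oxygen. The rule on readiness at baseline should be the same in both endpoints, so that the term keeps one meaning.
3. Say how stable saturation is judged at baseline, since one daily reading cannot show it.

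Requiring the criteria at two consecutive daily assessments is a debatable choice for the main definition and is better kept as a sensitivity analysis.

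The cost is wording and a derivation flag, to be set before unblinding. Section 4.5.4 already records temperature, respiratory rate, saturation and oxygen flow on Day 1 and daily in hospital. The downside is that for these patients the event depends partly on local discharge practice.
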